### 1.1. Trial Design Overview

This is a single-arm, single-center, open-label trial of azacitidine combined with pembrolizumab in subjects with locally-advanced or metastatic pancreatic adenocarcinoma. Thirty-one evaluable subjects will be enrolled to assess the efficacy and safety of combination therapy in the second- line setting.

All subjects will have received systemic first-line chemotherapy, 5-FU or gemcitabine-based combination or monotherapy, prior to enrollment on the study. Azacitidine daily for 5 days will be given every 4 weeks (28 days). Fixed-dose pembrolizumab will be administered every 3 weeks for up to approximately 2 years beginning 2 weeks after initiation of azacitidine. The primary efficacy endpoint will be progression-free survival among all enrolled subjects. Disease progression will be determined based on RECIST 1.1 criteria; however, patients will be permitted to continue therapy following the development of progression of disease by RECIST 1.1 criteria if considered clinically appropriate by the study principal investigator.

As preliminary data suggests there is minimal toxicity overlap between pembrolizumab and a hypomethylating agent, there will be an accelerated Phase 1 dose determination component of the study. In the initial cohort, low-dose azacitidine will be administered, as studied in patients with advanced or metastatic solid tumors, and pembrolizumab will be administered at fixed dose

as detailed in the protocol. An initial cohort of 6 subjects will be enrolled, treated with combination therapy, and assessed for safety. Following enrollment of the initial 6 evaluable subjects all toxicity data will be reviewed. If 2 or more patients experience a treatment related dose-limiting toxicity (DLT) within the first 6 weeks of treatment administration (Defined in Section 5.2), then accrual at that dose level will stop. We will allow for 1 dose reduction in azacitidine and if agreed by the PI, the study will resume at the lower dose (Dose -1) and will again accrue 6 subjects who will receive combination therapy. If 2 or more subjects experience treatment related DLTs at this level, we will discontinue the combination study.

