## 5. STUDY DESIGN

### 5.1. General Design

This is a single-arm, open-label, single site Phase II trial of azacitidine combined with pembrolizumab in previously systemically treated subjects with a histologically or cytologically confirmed diagnosis of pancreatic ductal adenocarcinoma. Pre-treatment biopsies will be required for those subjects without an archival sample. All subjects will be required to provide a tumor tissue sample, either from the primary or a metastatic site, for biomarker analysis after 8 weeks on treatment. Thirty-one evaluable subjects will be allocated to receive azacitidine 50 mg/m^2 SubQ for 5 days every 28 days (Q4W) with single-agent pembrolizumab 200 mg IV every 3 weeks (Q3W) beginning on week 3.

The primary objective of this trial is to determine the PFS of pembrolizumab given in combination with a hypomethylating agent. Beginning with screening, all imaging assessments will be evaluated using RECIST 1.1. On-study imaging assessments will be performed every 8

weeks (Q8W) calculated from the date of allocation and independent of treatment delays. RECIST 1.1 will be used by the site for treatment decisions until the first radiologic evidence of progressive disease (PD).

Following the first radiologic evidence of PD by RECIST 1.1, treatment decisions may be made by the adaptation of RECIST 1.1 as described in [Section 13.5](#) termed immune-related RECIST (irRECIST) to accommodate the tumor response patterns seen with pembrolizumab treatment (e.g., tumor flare). This was first described by Nishino, et al. 2013 and is further modified for the pembrolizumab program as described in [Section 13.5](#). For a clinically stable subject with first radiologic evidence of PD, it is at the discretion of the principal investigator to continue treating the subject with pembrolizumab until PD is confirmed at least 4 weeks after the date of the first tumor imaging confirming PD per the principal investigator. If radiologic PD is confirmed by the subsequent tumor imaging, the subject should be discontinued from treatment unless, in the opinion of the investigator, the subject is achieving a clinically meaningful benefit; an exception for continued treatment may be considered following consultation with the PI.

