Serum CA 19-9 e,h	X			X		X		X		X then Q6W		X			
HBV, HCV, HIV c,i	X														
Efficacy Measurements															
Tumor Imaging	X j						X k then Q8W					X l			
Tumor Biopsies/Archival Tissue Collection/Correlative Studies Blood															
Archival or Newly Obtained Tissue Collection m	X						X					X optional			
Correlative Studies Blood Collection	X n			X	X	X						X			

a. Unless otherwise specified, assessment/procedures are to be performed prior to dose administration on Day 1 of each cycle.

b. Subjects who discontinue study treatment without documented disease progression should continue to be monitored for disease by radiologic imaging every 8 weeks (□7 days) until (1) the start of new anti-cancer treatment, (2) disease progression, (3) death, or (4) the end of the study, whichever occurs first.

c. Informed consent will include consent for correlative studies including biopsies and serum collections.

d. For women of reproductive potential, a negative pregnancy test should be performed within 72 hours prior to first dose of trial treatment. Pregnancy tests (serum and/or urine tests) should be repeated if required by local guidelines.

e. Laboratory Screening Tests should be performed within 7 days prior to first dose of treatment. For all subjects, unresolved abnormal labs resulting in drug-related AEs should be followed until resolution. Post dose lab may be collected up to 72 hours prior to the scheduled timepoint.

f. Chemistry will be collected on Day 1 of each cycle of azacitidine and pembrolizumab.

g. CBC with differentials will be collected on Day 1 of each cycle of azacitidine and pembrolizumab.

h. On treatment CA 19-9 – starting at Cycle 1 of Pembrolizumab, CA 19-9 will be collected Q3W until week 15 then every 2 pembrolizumab cycles (Q6W +/- 2 weeks) through the end of treatment

i. All subjects will be tested for HIV, HBV, and HCV prior to enrollment. Those who are positive for HIV, untreated active Hepatitis B, and dual infection with HBV/HCV will be excluded.

j. Tumor imaging at screening: Imaging will be performed within 28 days prior to the first dose of induction. Imaging should include CT chest, abdomen, and pelvis or MRI if CT is clinically contraindicated.

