k. The first-on study tumor imaging will be performed after 8 weeks (± 7 days) of treatment, and will continue every 8 weeks (□□7 days) thereafter (or more frequently if clinically indicated). Timing of imaging follows calendar days and should not be adjusted due to dose interruptions. The same imaging technique, acquisition, and processing parameters for a subject should be used throughout the trial if possible.

l. Subjects without confirmed PD who discontinue treatment will have imaging performed at the time study treatment is discontinued (i.e. date of discontinuation □□4 week window). If a scan was obtained within 4 weeks prior to discontinuation of treatment, then imaging at treatment discontinuation is not required. Continue to monitor disease status as indicated in Section 6.6. Subjects who discontinue treatment after confirmed PD will not need further imaging performed during the follow-up period.

m. If archival tissue is not available then fresh biopsy is considered any tumor tissue collection within 42 days prior to first dose of study treatment and after previous therapy. All 31 subjects will have a newly-obtained biopsy during week 8 (□□7 days) of the study. An optional biopsy is also requested at the time of discontinuation for PD.

Trial Period:	Screening Phase	Treatment Cycles a										End of Treatment (last dose) or Discontinuation	Post-Treatment		
		Azacitidine (4 weeks per cycle)						Pembrolizumab (3 weeks per cycle)							
Treatment Week:		1	2	3	5	6	8	9	12	15	18		Safety Follow- Up (30 days from last dose) q	Follow Up Visits b (Q8W)	Survival Follow-Up (Phone)
Scheduling Window (Days):	-28 to -1	± 3	± 3	± 3	± 3	± 3	± 3	± 3	± 3	± 3	± 3			± 7	

n. Collect at baseline, and then on weeks 3, 5, and 6 prior to study treatment administration. Whole blood for Genetics/RNA and DNA analyses. Serum and plasma for Proteomics.  
o. The first dose of azacitidine is Week 1 Day 1, other doses have a +/-3 day window for dose administrations (for azacitidine as well as pembrolizumab). Azacitidine will be dosed on 5 consecutive business days. On the days when azacitidine is given with pembrolizumab, the pembrolizumab will be administered first followed by azacitidine.  
p. Screening ECOG should be performed within 3 days prior to first dose of study therapy.  

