**12.1.6.6                    Tumor Tissue Collection and Correlative Studies Blood Sampling**

All patients will have tumor biopsy specimens obtained at baseline prior to study drug administration and then during week 8 to assess methylation status and immune response. Peripheral blood will be evaluated for methylation status at baseline and then prior to treatment administration on weeks 3, 5, and 6.

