#### **13.6.3.2 Epigenetic effect in tumor tissue**

The premise of our proposal is that hypomethylation of tumor cells and/or stromal cells results in a significant polarization of the immune response seen in pancreatic cancer and this leads to an increase in response to tumor checkpoint inhibition. Our preliminary data provides strong support for this, however this study provides a unique opportunity to understand the dynamic changes that occur in the tumor. Therefore we will first assess the impact of the systemically administered demethylating agent on tumor tissue. This assessment is performed in all 31 patients 8 weeks after completion of TCI therapy. Core biopsies are obtained and tumor tissue is microdissected for methylation profiling using the Illumina 800K platform. Comparison is made to the pre-treatment tumor biopsy. The Herbert Irving Comprehensive Cancer Center Epigenetics Core Laboratory (led by co-investigator [name], PhD) routinely performs this procedure and the subsequent statistical analysis and mapping of the resulting data to ENCODE tracks. Validation of up to 48 amplicons in up to 48 samples is done using the Fluidigm Access Array – Illumina MiSEQ platform. Here, bisulfite treatment and sequencing is performed to validate “hits” from the methylation array.

A subsequent validation step at the transcriptional and translational level will be performed

based on the classes of genes identified but include one of three strategies (1) RNASeq; (2) Q-PCR; (3) immunohistochemistry or immunofluorescence on concurrent biopsy specimens. In cases where sufficient quantity of tumor material is obtained to perform RNASeq analysis this will be pursued. The parallel use of methylation and expression profiling allows for the selection of functionally most relevant genes. Although there is support for the feasibility of sufficient amount of high quality RNA obtained from endoscopic biopsies to perform RNASeq as we are uncertain whether in each case this will be feasible the alternative strategies may also be pursued.

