#### **15.2.7 Exploratory and Ancillary Studies**

See [Section 13.6.3](#) for description of correlative studies. All subjects will be required to agree to an on treatment biopsy after 8 weeks of therapy. Given the patient population and the likelihood that some subjects will have disease or clinical progression precluding biopsies we estimate that we will obtain on-treatment biopsy samples from a minimum of 20 subjects.

- 15.2.7.1 Global DNA Methylation will be assessed in all subjects at baseline and every 2 weeks for the first 8 weeks of study. We will estimate the disease control rates (DCR) and time to event endpoints (median PFS and median OS) for subjects who have methylation below the median compared to above the median at baseline. We will also estimate these outcomes for those who achieve low methylation (<10% methylation) compared to normal methylation ( $\geq 10\%$  methylation) after 8 weeks of therapy. We will also estimate these outcomes for those who achieve a change in methylation greater than the median compared to higher than the median at 8 weeks (compared to baseline).
- 15.2.7.2 Fisher's exact test will be performed to compare the disease control rate for the two groups. Kaplan-Meier estimates of the survival distribution for the two groups will be calculated, and the two groups will be compared using a log-rank test. Change in methylation in tumor tissue will be evaluated in 20 patients who undergo baseline and week eight biopsies and will be compared using the paired t-test or the Wilcoxon signed-rank test depending on the data distribution. With 20 patients, we will have 80% power to detect a change of 0.66 standard deviations given an alpha of 0.05.
- 15.2.7.3 Change in methylation in tumor tissue will be evaluated in subjects who undergo baseline and week 8 biopsies. We will describe changes in specific gene methylation patterns as described in [Section 13.6.3](#).
- 15.2.7.4 Immune phenotyping will be measured on the subjects who undergo an on-treatment tumor biopsy. We will provide descriptive tables of IHC expression of CD8/CD3 T cell ratio, CD86/CD68 macrophage ratio, PD1 expression. Samples will be compared between pre and post combination specimens in treated subjects using the paired t-test.

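### The plan defines baseline tissue for the paired tumor analyses inconsistently, and no rule requires archival samples to post-date first-line chemotherapy

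*Combined protocol and SAP*

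**What the plan says.** Three places let archival tissue stand as the baseline sample.

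- Section 5.1: "Pre-treatment biopsies will be required for those subjects without an archival sample".
- Flow chart (12.1), tissue row, which includes the screening visit: "Archival or Newly Obtained Tissue Collection".
- Footnote m to the flow chart applies when no archival tissue is available. It then sets a timing rule: "fresh biopsy is considered any tumor tissue collection within 42 days prior to first dose of study treatment and after previous therapy". No such rule is given for archival tissue, here or elsewhere.

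Two places point to newly taken tissue.

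- Section 12.1.6.6: "All patients will have tumor biopsy specimens obtained at baseline prior to study drug administration and then during week 8".
- Section 1.1 says that T-cell activity will be studied in fresh tissue taken before and during treatment.

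The on-treatment sample is always new: "All 31 subjects will have a newly-obtained biopsy during week 8" (footnote m). Prior treatment is universal: "All subjects will have received systemic first-line chemotherapy, 5-FU or gemcitabine-based combination or monotherapy, prior to enrollment on the study" (1.1).

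For the analysis, 13.6.3.2 compares on-treatment tissue with the pre-treatment biopsy and presents this as an assessment of what the demethylating agent does to the tumor. Sections 13.6.3.3 and 15.2.7.4 compare immune markers before and after treatment with a paired test. Section 15.2.7.2 says: "Change in methylation in tumor tissue will be evaluated in 20 patients who undergo baseline and week eight biopsies". It attaches 80% power for a change of 0.66 SD at alpha 0.05 to those 20 patients. No analysis by source or date of the baseline tissue is planned.

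**The concern.** A paired comparison isolates what happened between the two samples. If the first is an archival block taken before first-line chemotherapy, the interval contains that chemotherapy, the disease course since then, and eight weeks of study treatment. The paired test sees only the sum. With one arm, no control group can separate the parts.

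At stake are tumor methylation, the CD8/CD3 and CD86/CD68 ratios, and PD-1 expression. Pre- versus on-treatment infiltration is a named exploratory objective (2.3), tumor methylation change has its own power statement, and subjects are asked for a week 8 biopsy to support these analyses. A first-line effect could pass for a study-drug effect, or hide one. Footnote m shows that the authors thought sample timing relative to prior therapy mattered, since they impose it on fresh tissue.

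**Working it through.** **1. The plan's own figure.** Inputs from 15.2.7.2: 20 pairs, 0.66 SD, alpha 0.05, 80% power. Sidedness is not stated. For a two-sided paired t-test, power is the probability that a noncentral t with n − 1 degrees of freedom and noncentrality d√n exceeds the 0.975 t quantile in absolute value. With n = 20, d√n = 0.66 × √20 = 2.95 and power is 79.9%. The stated 80% reproduces. (One-sided it would be 88.5%; for the signed-rank test at relative efficiency 0.955, 77.9%.) The arithmetic is sound. What it assumes is that 20 pairs all measure change from a valid baseline.

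**2. If pre-chemotherapy baselines enter the test.** Let f be the share of pairs whose baseline predates first-line therapy, and b the shift first-line therapy caused, in SDs of the paired difference. The mean change is then biased by f × b; for example, f = 0.5 and b = 0.5 give 0.25 SD. Neither f nor b is in the documents, so both are assumptions and a range is shown. Simulated rejection rate with 20 pairs, no study-drug effect, two-sided 5% paired t-test, 40,000 runs:

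| Share of pairs affected | b = 0.25 | b = 0.5 | b = 1.0 |
|---|---|---|---|
| 0.25 | 5.8% | 7.6% | 14.4% |
| 0.50 | 8.1% | 17.3% | 46.9% |
| 0.75 | 12.3% | 34.1% | 84.8% |

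The bias can also run the other way. With a true study-drug change of 0.66 SD and an opposite first-line shift in half the pairs, power falls from 80% to 61% (b = 0.25) or 39% (b = 0.5).

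**3. If only qualifying baselines enter the test.** The same power formula with fewer pairs, where the number of qualifying pairs is again an assumption:

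| Qualifying pairs | d√n at d = 0.66 | Power at 0.66 SD | Change detectable with 80% power |
|---|---|---|---|
| 20 | 2.95 | 79.9% | 0.66 SD |
| 15 | 2.56 | 66.2% | 0.78 SD |
| 10 | 2.09 | 46.2% | 1.00 SD |

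Section 15.2.7 explains the drop from 31 subjects to at least 20 on-treatment samples only by progression that precludes biopsy. It makes no allowance for subjects whose only baseline tissue is archival.

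**4. Timing of the second sample.** Section 13.6.3.2 says: "This assessment is performed in all 31 patients 8 weeks after completion of TCI therapy". Section 5.1, footnote m, 12.1.6.6 and 15.2.7 all place the biopsy at about week 8 of treatment. The abbreviation TCI is not explained. This is a separate wording conflict, but it concerns the other half of the same pair.

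**The case against.** The strongest reply is that the text closest to the paired analyses speaks of biopsies, not archival blocks. Section 12.1.6.6 describes baseline specimens in all patients for methylation and immune response, 15.2.7 restricts tumor methylation change to subjects who undergo both biopsies, and 13.6.3.2 compares with a pre-treatment biopsy. Section 3.14 gives archival material a use of its own, expression profiling. On that reading no pre-chemotherapy tissue enters the paired tests. This is a fair reading, and it is why the point is a conflict with a conditional consequence. It does not settle the matter: 5.1, the flow chart and footnote m say otherwise, and 10.6 describes a pre-screening step to establish archival tissue status.

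A reader might infer that archival blocks usually predate first-line therapy, so that the paired results will be confounded. The documents do not say so. Section 6.1 admits subjects who recur within 6 months of neoadjuvant or adjuvant chemotherapy, and tissue from a resection after neoadjuvant therapy or from a biopsy at recurrence would post-date it.

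It is also fair that the effect may be small: a quarter of pairs shifted by 0.25 SD gives 5.8% against a nominal 5%. And these are exploratory analyses, some of them largely descriptive (15.2.7.4).

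**Conclusion.** The concern stands in a limited form. The documents conflict on which tissue is the baseline. Under 5.1, the flow chart and footnote m, any archival sample that predates first-line chemotherapy makes the pre/week 8 change a mixture that 13.6.3.2 would credit to the demethylating agent. The size is unknown. False-positive rates of 6% to 14% (a quarter of pairs affected) or 8% to 47% (half affected) rest on assumed shifts of 0.25 to 1.0 SD of the paired difference.

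Three stronger readings are not supported. The power statement is not wrong; it holds if 20 pairs qualify. The trial's main conclusions are not touched: PFS, its sample size, the secondary endpoints and blood methylation do not use this tissue comparison. And a post-chemotherapy baseline would not make the change attributable to azacitidine. It would still combine both study drugs and disease course in a single arm, and section 6.2 bars chemotherapy only within 14 days of first dose, so tissue within the 42-day window may still reflect recent chemotherapy. The fix removes one avoidable source of confounding, not all of them.

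**What to change.** - In 13.6.3.2, 13.6.3.3 and 15.2.7, define the main paired analysis as pairs whose baseline tissue was taken after the end of prior therapy and within 42 days before first dose, the condition footnote m already sets for fresh tissue.
- Record the source and collection date of each baseline sample relative to prior therapy. Show the remaining archival pairs separately, as a sensitivity analysis.
- State the 0.66 SD and 80% power sentence as conditional on 20 qualifying pairs, and give the 15-pair and 10-pair figures beside it.
- Reconcile 1.1, 5.1, 12.1.6.6 and footnote m on baseline tissue, without adding biopsies for this purpose.
- Reconcile the sample timing in 13.6.3.2 with the week 8 on-treatment time point used elsewhere.

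The cost is wording and one or two recorded data items. The downside is fewer pairs in the main comparison and a larger detectable change. If few subjects lack archival tissue, the qualifying pairs may also be a selected subset, and the report should say so.

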## 1. PROTOCOL SYNOPSIS

This document is a protocol for a human research study. This study is to be conducted according to US and international standards of Good Clinical Practice (FDA Title 21 part 312 and International Conference on Harmonization guidelines), applicable government regulations and Columbia University Medical Center institutional research policies and procedures.

Title	Phase II open-label, single-center study evaluating safety and efficacy of pembrolizumab following induction with the hypomethylating agent azacitidine in patients with locally advanced or metastatic pancreatic cancer after failure of first-line therapy.
Protocol Number	AAAR3554
Trial Phase	2
Methodology	This is a single arm, open-label phase II trial of combination azacitidine and pembrolizumab in patients with locally advanced or metastatic pancreatic cancer in order to evaluate safety and efficacy. The primary endpoint is progression-free survival.
Study Duration	We estimate that the trial will require approximately 24 months to complete, with up to 18 months accrual and an additional 6 months follow-up to evaluate the primary efficacy outcomes for all subjects.
Study Center(s)	Columbia University Medical Center
Objectives	

Primary objective: To evaluate the progression-free survival per RECIST 1.1.

Secondary Objectives:

Safety Objective: To determine the safety and tolerability of induction therapy with azacitidine followed by pembrolizumab in advanced pancreatic cancer.

To evaluate the overall response rate (ORR), duration of response (DOR), disease control rate (DCR), and time to progression (TTP) per RECIST 1.1, and OS.

Number of Subjects	31 evaluable subjects will be enrolled overall
Diagnosis and Main Inclusion Criteria	Locally advanced or metastatic pancreatic cancer who progressed on a single line of 5-FU- or gemcitabine-based chemotherapy.
Study Product, Dose, Route, Regimen	

Pembrolizumab 200 mg IV every 3 weeks until progression

Azacitidine 50 mg/m^2 subcutaneous daily for 5 days every 28 days

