Duration of administration	Treatment will continue until progressive disease, unacceptable adverse events, intercurrent illness that prevents further administration of treatment, investigator's decision to withdraw the subject, subject withdrawal of consent, pregnancy of the subject, noncompliance with trial treatment or procedure requirements, subject receives 35 treatments (approx. 2 years) of pembrolizumab, or administrative reasons requiring cessation of treatment.
Reference therapy	Not applicable – Single arm study.
Statistical Methodology	This is a single arm, phase II study. To detect an improvement in progression free survival from a historical control of 2 months to 4 months, with a one-sided p-value of 0.05 and 80% power, 31 evaluable patients will be required. We anticipate accrual over 18 months with an additional 6 months required for follow-up.

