### **6.5.1 When and How to Withdraw Subjects**

Subjects may withdraw consent at any time for any reason or be dropped from the trial at the discretion of the investigator should any untoward effect occur. In addition, a subject may be withdrawn by the investigator or the Sponsor if enrollment into the trial is inappropriate, the trial plan is violated, or for administrative and/or other safety reasons.

A subject must be discontinued from the trial for any of the following reasons:

- The subject or legal representative withdraws consent.
- Confirmed radiographic disease progression
  - *Note:* A subject may be granted an exception to continue on treatment with confirmed radiographic progression if clinically stable or clinically improved.
- Unacceptable adverse experiences
- Intercurrent illness that prevents further administration of treatment
- Investigator's decision to withdraw the subject
- The subject has a confirmed positive serum pregnancy test
- Noncompliance with trial treatment or procedure requirements
- The subject is lost to follow-up
- Completed 24 months of uninterrupted treatment with pembrolizumab or 35 administrations of study medication, whichever is later.
  - *Note:* 24 months of study medication is calculated from the date of first dose. Subjects who stop pembrolizumab after 24 months may be eligible for up to one year of additional study treatment if they progress after stopping study treatment after consultation with the sponsor.

- Administrative reasons

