### 13.5. Assessment of Disease According to Immune Related RECIST for Solid Tumors

Although this will not be the primary endpoint we will allow subjects to remain on study if they meet the criteria for immune related RECIST as described. The immune related RECIST (irRECIST), is adapted to account for the unique tumor response seen with immunotherapies.

The irRECIST criteria considers index lesions identified at baseline together with new lesions that may occur after the start of treatment and are incorporated into the calculated tumor burden. The appearance of new lesions alone does not constitute PD.

If imaging shows PD, tumor assessment should be repeated 4 weeks later to confirm PD with the option of continuing treatment for clinically stable subjects. Clinically stable will be defined by the following criteria:

- Absence of signs and symptoms indicating disease progression
- No decline in ECOG performance status

- Absence of rapid progression of disease
- Absence of progressive tumor at critical anatomical sites (eg, cord compression) requiring urgent alternative medical intervention
- Absence of disease progression in close proximity to a vital organ.

Subjects must meet the above bulleted criteria for clinically stable disease in order to continue on study treatment beyond initial imaging showing PD. Clinically stable subjects who continue on study treatment will first be reconsented.

In determining whether the tumor burden has increased or decreased, investigators should consider all target lesions as well as non-target lesions. Subjects who are deemed clinically unstable are not required to have repeat imaging for confirmation. If radiologic progression is confirmed, then the subject will be discontinued from study treatment as specified in the Protocol, and the first radiographic evidence of PD should be the date of progression. If radiologic progression is not confirmed, then the subject should resume/ continue study treatment and have their next scan according to the Protocol-specified schedule (ie 4 weeks later and then every 8 weeks). If progression is not confirmed and the subject continues on treatment, the next scan that documents disease progression (and is confirmed by a second scan at least 4 weeks later) will be considered the date of disease progression.

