NOTE: If a subject with confirmed radiographic progression (ie, 2 scans at least 28 days apart demonstrating PD) is clinically stable or clinically improved, and there is no further increase in the tumor dimensions at the confirmatory scan, an exception may be considered to continue treatment upon consultation with the sponsor. In order for a patient to be considered clinically stable, all bulleted criteria listed above in section 13.5 must be fulfilled. Clinically stable subjects should also have at the confirmatory scan no further increase in the target lesions, no unequivocal increase in non-target lesions, and no additional new lesions develop (non-worsening PD) to continue study treatment. Such exceptions will need to be made in consultation with the study Sponsor and the trial's DSMC. However, study treatment continued beyond PD will be discontinued if radiologic progression worsens.

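### The protocol sets conflicting conditions for continuing treatment after first and after confirmed progression

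*Combined protocol and SAP*

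**What the plan says.** **First progression**

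- The synopsis gives the regimen as "Pembrolizumab 200 mg IV every 3 weeks until progression" and the duration as "Treatment will continue until progressive disease, unacceptable adverse events". Section 8.6 likewise lists disease progression as an end of therapy. None of the three mentions a confirmation step or an exception.
- Section 1.1 permits therapy to continue "following the development of progression of disease by RECIST 1.1 criteria if considered clinically appropriate by the study principal investigator".
- Section 5.1 leaves continuation of pembrolizumab in a clinically stable subject to the principal investigator's discretion until progression is confirmed. It says that decisions may follow the adapted criteria in 13.5.
- Section 13.5 lists five criteria for clinical stability and states: "Subjects must meet the above bulleted criteria for clinically stable disease in order to continue on study treatment beyond initial imaging showing PD". It also requires re-consent before treatment goes on.

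**Confirmed progression**

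- Section 5.1 stops treatment unless the investigator judges that the subject has clinically meaningful benefit, in which case "an exception for continued treatment may be considered following consultation with the PI". The next paragraph of 5.1 allows pembrolizumab only until progression is confirmed and states no exception.
- Section 6.5.1 makes confirmed progression a reason for mandatory discontinuation, with a note: "A subject may be granted an exception to continue on treatment with confirmed radiographic progression if clinically stable or clinically improved". It names no approver.
- The note in 13.5 requires the subject to be clinically stable or improved, with no increase in tumour dimensions at the confirmatory scan. For subjects classed as clinically stable it also requires all five criteria, no unequivocal non-target increase and no additional new lesions. It adds: "Such exceptions will need to be made in consultation with the study Sponsor and the trial's DSMC".

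**The concern.** Whether a subject stays on two experimental drugs after progression depends on which section the treating physician reads. Re-consent and the DSMC consultation tied to this decision appear only in 13.5. They attach to different moments: re-consent to continuing past the first progression scan, DSMC input to the exception after confirmed progression. The trial is run at one centre by a sponsor-investigator, so consulting the PI and consulting the Sponsor may amount to the same thing. The differences of substance are then the DSMC step, the lesion condition, the stability criteria and re-consent.

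Four things are at stake: the protection of subjects whose cancer is progressing, the exposure over which toxicities are counted, the interpretation of OS when time on treatment after progression varies, and whether a given continuation is a protocol deviation. Section 14.3 sends deviations to the DSMC, but whether a continuation is one depends on the section applied.

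**Working it through.** No planned figure rests on this point, so the check sets the rules side by side and runs the same subject through each.

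| Section | First progression | Confirmed progression |
|---|---|---|
| Synopsis, 8.6 | Therapy ends | Therapy ends |
| 1.1 | PI judgement | Not separately addressed |
| 5.1 | Clinically stable, PI discretion; permissive pointer to 13.5 | Perceived benefit, PI consulted; next paragraph has no exception |
| 6.5.1 | Not addressed | Stable or improved; approver not named |
| 13.5 | Five criteria, re-consent | Stable or improved, no further growth, Sponsor and DSMC consulted |

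**Case A.** First progression, ECOG status has declined, PI thinks continuation appropriate. Section 1.1 permits it. Section 13.5 does not, because one of its five criteria fails. Section 8.6 and the synopsis end therapy.

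**Case B.** Confirmed progression, target lesions larger at the confirmatory scan, investigator sees benefit. Section 5.1 permits continuation after the PI is consulted. Section 13.5 does not permit it. Section 6.5.1 permits it if the subject is clinically stable or improved.

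**Case C.** Confirmed progression, all five criteria met, no further growth or new lesions. Section 6.5.1 permits continuation, and so does 5.1 if benefit is seen; neither mentions the DSMC. Section 13.5 requires Sponsor and DSMC consultation. Section 8.6 and the second paragraph of 5.1, read literally, end treatment.

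**Drugs covered.** The first-progression sentence in 5.1 names only pembrolizumab, while 13.5 speaks of study treatment. Whether azacitidine continues at that stage is therefore unclear. The confirmed-progression sentence in 5.1 refers to treatment generally.

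**Upper bound on subjects affected.** Inputs: 31 subjects, 18 months' accrual, 6 months' further follow-up, and median PFS of 2 months (historical) or 4 months (target), from 15.2.5. Assumptions not in the plan: uniform accrual, exponential PFS, no loss to follow-up. Follow-up is then uniform on 6 to 24 months, and with λ = ln 2 / median:

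mean S = (e^(−6λ) − e^(−24λ)) / (18λ); expected events = 31 × (1 − mean S)

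- Median 2 months: λ = 0.3466; mean S = (0.1250 − 0.0002) / 6.238 = 0.020; events = 31 × 0.980 = 30.4.
- Median 4 months: λ = 0.1733; mean S = (0.3536 − 0.0156) / 3.119 = 0.108; events = 31 × 0.892 = 27.6.

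These are all PFS events. Deaths without progression, and subjects already off treatment when they progress, do not reach the continuation decision.

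**The case against.** The strongest reply is that the sections can be read together. Section 5.1 refers to 13.5 and uses a term, clinically stable, that 13.5 defines. Section 1.1 is only an overview. Section 8.8 sends removal decisions to 6.5.1, which holds the exception missing from 8.6. The note in 6.5.1 uses the same stable-or-improved test as 13.5 and reads mostly as an abbreviation of it. Permissive wording that omits a step does not say the step is unnecessary.

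Much of this stands. At first progression, 5.1 and 13.5 can be harmonised, and 6.5.1 alone would be a drafting gap. But the pointer in 5.1 is only permissive, and 1.1, 6.5.1 and 8.6 have none. At confirmed progression 5.1 states its own criterion and its own consultation, so case B is a contradiction and not an omission. Nor does meeting 13.5 automatically satisfy 5.1, whose benefit test 13.5 lacks. The protocol does not say which section prevails.

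A reader might also infer that continuation outside 13.5 would have no independent oversight. The documents do not support that: under 14.3 the DSMC monitors every treated subject for toxicity and reviews deviations, and 14.4 provides independent compliance monitoring. What the other sections lack is the check tied to this decision.

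**Conclusion.** The protocol contradicts itself on treatment after progression. The conflict is sharpest at confirmed progression between 5.1 and 13.5, and at first progression between 1.1, 13.5 and the unqualified stopping statements in 8.6 and the synopsis. This rests on the text alone and on no numerical assumption.

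Two stronger readings should be resisted. The first is that the primary analysis is compromised. Section 13.6.1.1 dates PFS at first documented RECIST 1.1 progression or death, so the choice between continuation rules does not by itself move the event date. The second is that nearly every subject is affected. The 28 to 30 of 31 is a ceiling under the stated assumptions. The documents give no basis for estimating how many subjects would still be on treatment at radiographic progression, or for how many of those the sections would give different answers.

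The point should be corrected because it bears on subject protection, exposure and toxicity counts, OS interpretation and the definition of a deviation.

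**What to change.** Reconcile the passages into one rule for first progression and one for confirmed progression. Each should state the clinical and lesion criteria, whether re-consent is needed, who must agree, and which of the two drugs may continue. Hold both rules in a single section and have 1.1, 5.1 (both paragraphs), 6.5.1, 8.6 and the synopsis refer to it as binding. Record on the CRF the date of first RECIST 1.1 progression and, for each continuation, the conditions met. Which conditions apply is for the sponsor to decide.

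The cost is amendment wording and a small CRF addition. Sample size, endpoint definition and visit schedule need not change.
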